### **9.2.2 Selection of population**

#### **9.2.2.1 Inclusion/ exclusion criteria**

Patients who fulfil the following criteria will be included.

- Patients who have been diagnosed with chronic obstructive pulmonary disease (chronic bronchitis, emphysema) by physician and need to be treated co-administration of a long-acting inhalational anticholinergic and a long-acting inhalational β2-agonist to relief of various symptoms associated with the obstructive impairment of airways
- Patients who are prescribed Tio+Olo FDC 5µg/5µg for the first time

Patients who present the following criteria will be excluded.

- Patients who have been registered once in this study (i.e., re-entry of patients is not allowed).
- Patients who are participating or registry in a clinical trial.
- Patients who have a contraindication to Tio+Olo FDC 5µg/5µg defined in the package insert for Tio+Olo FDC 5µg/5µg.

#### **9.2.2.2 Registration period**

From August 2016 to August 2017

#### **9.2.2.3 Patient registration method**

Patients will neither be selected randomly nor assigned to treatment randomly. At each study site, patients who are judged by investigator eligible to the study will be consecutively registered. Investigators register patients sequentially who are prescribed Tio+Olo FDC

5µg/5µg treatment according to regular medical practice to reach the number of contract with site.

Patients will be registered by entering necessary information into the EDC immediately or within 14 days whenever possible from the day of treatment initiation (inclusive). The necessary information for registration is gender, date of birth, start date of administration and the reason for use.

Investigators will use a signed form to confirm that the patients will be registered continuously at the site.

#### End of registration

Patient registration will be stopped when the target number of study is reached. A log of all patients included into the survey will be maintained at the sites.

### **9.2.3 Discontinuation of the study by the sponsor**

reserves the right to discontinue the study overall or at a particular study site at any time for the following reasons:

1. Failure to meet expected enrolment overall goals or goals at a particular study site,
2. Emergence of any efficacy/safety information that could significantly affect continuation of the study or any other administrative reasons.
3. Violation of GPSP, the NIS protocol, or the contract by study site or investigator, disturbing the appropriate conduct of the study.

The study site will be reimbursed for reasonable expenses incurred in case of study termination (except in case of the third reason).

### **9.2.4 Priority survey items**

The following outcomes of interest are set with particular priority as priority survey items.

- Cardiovascular adverse events
- Anticholinergic-related adverse events
- Beta2 agonist-related events

## **9.3 VARIABLES**

### **9.3.1 Exposure**

Exposure to Tio+Olo FDC 5µg/5µg is estimated as time from the day Tio+Olo FDC 5µg/5µg is initiated until the day the drug is last administrated on a patient-level (or the final contact with the patient during the regular observation period).

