## **9. RESEARCH METHODS**

### **9.1 STUDY DESIGN**

This is an observational study based on newly collect real-world data (i.e., data under real-world practice) to evaluate safety and effectiveness of Tio+Olo FDC 5µg/5µg in patients with chronic obstructive pulmonary disease (chronic bronchitis, emphysema).

The study will be initiated after marketing of Tio+Olo FDC 5µg/5µg in Japan. The study will consist of a baseline visit and further visits in a 52-week follow-up for patients who have initiated the Tio+Olo FDC 5µg/5µg treatment.

As this is an observational study, no specific treatment is mandated or withheld from the patients. The choice of maintenance treatment for chronic obstructive pulmonary disease (chronic bronchitis, emphysema) must be according to regular medical practice and at discretion of physician (i.e., no randomised assignment of patient to treatment [Tio+Olo FDC or other treatment] is performed). In total, approximately 1100 patients are planned to be registered at approximately 200 study sites in the study.

Patients participating in the subsequent follow-up will undergo regular observations. These observations should be reported after 4, 12, 24 and 52 weeks since the initiation of Tio+Olo FDC 5µg/5µg as long as they continue to receive the treatment. Patients will not be followed any longer once they are reported to have discontinued the Tio+Olo FDC 5µg/5µg treatment. Patients who experience adverse events will be followed up until detailed information on the outcome of the adverse event is collected.

The primary outcome of this study is the incidence and exposure-time adjusted incidence rate of adverse drug reactions (ADRs).

The secondary outcome of this study is:

- COPD assessment test (CAT) at 12 weeks.

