### 9.7.2 Analyses of Safety

The safety analysis will include all patients registered in the study and receiving the Tio+Olo FDC 5µg/5µg treatment except for patients who meet the ineligible criteria (see section 9.7). In general, safety analyses will be descriptive in nature, be based on BI standards, and focus on AEs related to the Tio+Olo FDC 5µg/5µg treatment.

AEs will be coded using the current version of the Medical Dictionary for Drug Regulatory Activities (MedDRA) and will be based on the concept of treatment emergent AEs. To this end, all AEs occurring between the initiation of Tio+Olo FDC 5µg/5µg prescribed at baseline visit and 21 days (inclusive) after the last administration will be considered 'treatment emergent'. An AE is considered to be an ADR if either the physician/investigator who has reported the AE or the sponsor assesses its causal relationship as 'related'.

The incidence (n and % in treatment group) and treatment exposure time adjusted incidence rate (n in 100 patient years) of AEs in patients treated with Tio-Olo FDC (treatment emergent including 21 days after discontinuation of Tio+Olo FDC medication) will be tabulated by MedDRA SOC and PT for overall and for subgroups based on the important baseline characteristics, if sample size allows (see 9.3.3)

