 - ICS+LAMA+LABA (free combination + fixed dose combination): Yes, No
 - Other respiratory medication
 - Theophylline: Yes, No
 - Mucolytic: Yes, No
- Previous therapy: Yes, No, Unknown

- Concomitant therapy: Yes, No, Unknown

Treatment exposure:

- Duration of Spiolto Respimat treatment [days] = (date of last treatment intake) - (date of first intake) + 1
If after the data lock, Spiolto Respimat is ongoing and date of last treatment intake is missing: date of last treatment intake = Latest date in book
- Duration of Spiolto Respimat treatment class [weeks]: <= 4 weeks, 4 to <= 12 weeks, 12 to <=24 weeks, 24 to <=52 weeks, > 52 weeks.
Note: In terms of days <= 29days, 29 to <= 85days, 85 to <= 169, 169 to <= 365, >365

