6. GENERAL ANALYSIS DEFINITIONS

6.1 TREATMENT(S)

For basic information on treatment in the study, please refer to NIS Protocol Section 4. The technical specification for treatment set-up is described in the Analysis Data Set (ADS) plan.

For safety analyses, data up to 21 days after last treatment intake during observation period will be considered as on treatment for AE.

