7.8.1 Adverse events

Unless otherwise specified, the analyses of adverse events will be descriptive in nature. All analyses of AEs will be based on the number of patients with AEs and NOT on the number of AEs.

For further details on summarization of AE data, please refer to the guideline 'Analysis and Presentation of Adverse Event Data from Clinical Trials (1)

AE analyses will be carried out after integrating AE data from CRF and AE data from perceive system. In addition, AEs coded as “no adverse event” will not be included in the AE analyses.

The analysis of adverse events will be based on the concept of treatment emergent adverse events. That means that all adverse events occurring between first drug intakes till 21 days after last drug intake during observation period will be analysed. For details on the treatment definition, see Section 6.1.

An overall summary of adverse events will be presented.

The frequency of patients with AEs, ADRs, SAEs and SADR will be summarised by primary system organ class and preferred term. Patients with ‘priority survey items’ according to the drug’s Risk Management Plan will be summarised separately. The analysis of “priority survey items”, “Important identified risks”, “Important potential risks” will be conducted for AEs, ADRs.

It is created that table of patient with ADRs in each subgroup defined in Section 6.4. Not only the frequency but also the odds ratios are displayed.

In addition summaries for the time to onset of first episode for the ADRs will be tabulated, by duration (<= 4 week, 4 to <= 12 weeks, 12 to <=24 weeks, 24 to <=52 weeks, > 52), by primary system organ class and preferred term.

Adverse events leading to death and adverse events leading to discontinuation will be also summarised by treatment, primary system organ class and preferred term.

An ADR is defined as an AE for which either the investigator or the sponsor (or both) assess the causal relationship to Spiolto Respimat as “Yes”. A SAE is defined as an AE for which either the investigator or the sponsor (or both) assess the seriousness either as “Serious”.

The system organ classes will be sorted according to the standard sort order specified by EMA, preferred terms will be sorted by frequency (within system organ class).

The following AEs are detected on the basis of the Standardised MedDRA queries (SMQs) or Boehringer Ingelheim customised MedDRA query (BICMQ) (details are described in ADS plan).

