Safety will be assessed by treatment exposure time adjusted incidence rate (n in 100 patient years) of ADRs.

Priority survey items

- Cardiovascular adverse events
- Anticholinergic-related adverse events
- Beta2 agonist-related events

Important identified risks

- Cardiac failure
- Atrial fibrillation and extra systoles
- Ileus, Angle closure glaucoma
- Anaphylaxis

Important potential risks

- Cardiac disorder (Myocardial ischaemia, Cardiac arrhythmia)

- Intubation and mortality related to asthma

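### The numerator of the exposure-adjusted ADR rate runs to 21 days after last intake, but neither definition of exposure time adds those 21 days, so the rate is slightly overstated if first ADRs are captured in that tail

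*Protocol*

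**What the plan says.** Protocol 9.1 sets the primary outcome: "The primary outcome of this study is the incidence and exposure-time adjusted incidence rate of adverse drug reactions (ADRs". The second part is the one at issue.

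**Numerator window.** Protocol 9.7.2 builds the tail into the description of the rate itself: "treatment exposure time adjusted incidence rate (n in 100 patient years) of AEs in patients treated with Tio-Olo FDC (treatment emergent including 21 days" after stopping. SAP 6.1 agrees: "data up to 21 days after last treatment intake during observation period will be considered as on treatment for AE". So does SAP 7.8.1: "all adverse events occurring between first drug intakes till 21 days after last drug intake during observation period will be analysed". SAP 7.8.1 also says that AE analyses count patients, not events.

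**Exposure time.** There are two definitions. Protocol 9.3.1 runs from initiation "until the day the drug is last administrated on a patient-level (or the final contact with the patient during the regular observation period". SAP 5.4 has "Duration of Spiolto Respimat treatment [days] = (date of last treatment intake) - (date of first intake) + 1", and for patients still on drug with no last-intake date, "date of last treatment intake = Latest date in book". Neither adds 21 days.

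**The rate.** SAP 7.8.1 says "Safety will be assessed by treatment exposure time adjusted incidence rate (n in 100 patient years) of ADRs" and names no other denominator. SAP section 4 declares no change from the protocol's analysis, so the Protocol 9.3.1 definition stands.

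**Observation after stopping.** Protocol 11.2 requires AE collection for 21 days after last intake. Protocol 9.1 ends follow-up once discontinuation is reported, Protocol 9.4 has the final casebook sent at discontinuation, and Annex 2 schedules no later visit.

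**The concern.** In a person-time rate, the numerator and the denominator should cover the same period. Here a patient who stops the drug can be counted for a first ADR on any of the next 21 days, while none of those days enters the patient-years. The bias is upward, and its size depends on how many patients stop, how early they stop, and how much of the tail is captured.

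The gap is widest for early stoppers. For a patient who stops at day 29, the omitted tail is 21/50 = 42% of the AE window; at day 365 it is 21/386 = 5%. Protocol 9.7.2 also plans the rate by subgroup, where differences in early stopping could matter somewhat more.

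What is at stake is the reproducibility and a small bias of one part of the primary outcome. Two analysts who resolve the gap differently would report slightly different rates from the same data.

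**Working it through.** The plan states no expected ADR rate, patient-years or discontinuation share, so it has no figure of its own to reproduce on this point. The sample-size figures in Protocol 9.5 concern the proportion with serious cardiovascular events and do not use person-time.

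**Step 1: set the periods side by side.**

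| Item | Source | Ends at |
|---|---|---|
| Events counted | Protocol 9.7.2; SAP 6.1, 7.8.1 | last intake + 21 days |
| Exposure, protocol | 9.3.1 | last administration, or final contact |
| Exposure, SAP | 5.4 | last intake, or latest date in the book if ongoing |

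**Step 2: formula.** Let q be the share who discontinue, E the mean days on drug, and h a constant event rate. Give a fully observed 21-day tail to discontinuers only. Events are counted over E + 21q days per patient and divided by E, so the reported rate is h × (1 + t), with t = 21q/E. No rule in the documents stops person-time at a first ADR, so E is full time on drug.

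**Step 3: inputs.** From the documents: the 21 days, 365 planned days (SAP Table 6.7:1) and 1000 patients (Protocol 9.5). Assumed: q from 10% to 50%, and the stopping pattern.
- Uniform stopping over days 1-365: E = 183q + 365(1 − q).
- Exponential stopping: E = q/λ, with λ = −ln(1 − q)/365.
- Extreme case, q = 0.5 and all stopping at day 29: E = 0.5 × 29 + 0.5 × 365 = 197.0.

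**Step 4: results.**

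| q | Tail patient-years per 1000 (1000 × 21q/365) | E uniform, t | E exponential, t |
|---|---|---|---|
| 0.1 | 5.8 | 346.8, 0.61% | 346.4, 0.61% |
| 0.3 | 17.3 | 310.4, 2.03% | 307.0, 2.05% |
| 0.5 | 28.8 | 274.0, 3.83% | 263.3, 3.99% |

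Extreme case: t = 10.5/197.0 = 5.33%. On-drug time runs from 950.1 patient-years (q = 0.1, uniform) to 721.3 (q = 0.5, exponential). A true rate of 5 per 100 patient-years would read 5.03 to 5.20; a true 20 would read 20.12 to 20.80.

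**Step 5: why this is an upper range.** Patients are counted once, so someone with an ADR before stopping adds nothing in the tail. If one third of discontinuers already had an ADR (assumed), 2.03% × 2/3 = 1.35% and 3.99% × 2/3 = 2.66%. With half the event rate in the tail, the range is 0.30% to 1.99% (2.66% in the extreme case). With no tail events captured, it is zero.

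**Step 6: the reverse error.** Crediting all 21 days when none is observed changes the rate by 1/(1 + t) − 1, which is −0.6% to −3.8% (−5.1% in the extreme case).

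**Step 7: scale.** Exact Poisson 95% limits relative to the estimate are −26% to +32% with 50 ADR patients and −19% to +22% with 100.

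**The case against.** The best defence is that the denominator is merely unnamed. SAP 5.4 never says its duration feeds the rate; it sits with the exposure classes and suits the extent-of-exposure table in SAP 7.7. SAP 7.8.1 refers to SAP 6.1 for the treatment definition, and SAP 6.1 calls the 21 days on treatment for AEs. The technical set-up is deferred to the ADS plan and AE summarisation to a guideline; neither is available here, and either may contain a person-time rule. Dividing by time on drug is also an interpretable measure, and the final-contact alternative in Protocol 9.3.1 may take in part of the tail.

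Much of this is fair. A reader might infer that the sponsor will certainly report an inflated rate; the documents do not show that. The point still stands on the text. Protocol 9.3.1 defines exposure, Protocol 9.7.2 attaches the tail to a rate adjusted for exposure, and SAP 6.1 extends the period for AE data without changing either duration. Final contact is confined to the regular observation period and is not a 21-day rule. If the two periods are meant to differ, nothing says so.

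A second tempting reading gives every patient a tail, which would raise the figure to 6.1-9.9% (10-50% stopping early at a mean of day 60-180, assumed). The documents do not support that. Patients still on drug have not stopped, and SAP 5.4 places their last intake at the latest date in the book, so the casebook holds nothing later for them.

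It is also tempting to cut both numerator and denominator at the end of AE observation actually made. That could drop ADRs which Protocol 9.7.2 and SAP 7.8.1 require, including any from the second AE source that SAP 7.8.1 merges in. The two parts of the primary outcome would then have different numerators, and the cut-off date may not be recorded.

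**Conclusion.** The mismatch is real as written, and minor. The rate is overstated to the extent that first ADRs are captured in the tail: at most about 0.6-4.0%, or 5.3% if half the cohort stops at day 29. That range assumes 10-50% discontinuation, a constant event rate, a fully observed tail and tails for discontinuers only; none of these comes from the documents. The actual figure would be lower, since earlier ADR patients are not counted again, and zero if nothing is captured after stopping.

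The effect is small beside sampling error in a descriptive, single-cohort study with no confirmatory test. A reader might infer that the primary outcome as a whole is compromised. It is not: the crude incidence uses no person-time, and the sample size and planned odds ratios do not depend on it. Confidence is moderate, because the ADS plan or the AE guideline may already settle the rule.

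**What to change.** 1. In SAP 7.8.1, define the denominator of the rate as time at risk from first intake to the earliest of last intake + 21 days, death, or data cut-off (latest date in the book if treatment is ongoing).
2. Leave the numerator as Protocol 9.7.2 and SAP 7.8.1 define it, so that it matches the crude incidence.
3. Keep the SAP 5.4 duration for the extent-of-exposure table.
4. Reconcile Protocol 9.1 with 11.2, so that it is clear whether AEs are observed for 21 days after stopping.
5. Because of that conflict, add one sensitivity rate matched without the tail: patients with an ADR up to last intake, over the SAP 5.4 duration. It needs only the intake dates already used.
6. If the ADS plan or AE guideline already sets this rule, cite it in the SAP.

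The cost is one derived variable, one extra table and a few sentences. The downside is a slight understatement of the main rate if the tail is not fully observed, bounded under the same assumptions by the 0.6-3.8% (5.1% in the extreme case) shown in step 6. The sensitivity rate would show whether this matters.

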### **9.3.2 Outcomes**

The following events are considered important outcomes.

#### Safety:

Safety will be assessed with the incidence (n and % in treatment group) and treatment exposure time adjusted incidence rate (n in 100 patient years) of AEs in patients treated with Tio+Olo FDC (treatment emergent). Results will be stratified by different treatment types prior to baseline and age as a general risk factor.

- Adverse Drug Reactions (ADRs) (primary outcome) : related AEs as judged by the investigator or sponsor with a suspected causal relationship with the Tio+Olo FDC 5µg/5µg treatment
- AEs leading to death
- AEs leading to discontinuation of the Tio+Olo FDC 5µg/5µg treatment)
- Serious Adverse Events(SAEs)
- Priority survey items: Cardiovascular adverse events, Anticholinergic-related adverse events, Beta2 agonist-related adverse events

Section 11 covers how to assess and report AEs including the definitions.

Additional subgroup analyses/ safety outcomes might be included based on new information that could become available during the course of the study.

#### Effectiveness:

##### Patient's global rating (PGR)

Patients will be asked to rate their health (respiratory condition) at 4 weeks, 12 weeks, 24 weeks and 52 weeks (compared to the day before they commenced treatment with study drug) on the following 7-point scale.

1	2	3	4	5	6	7
very much better	much better	a little better	no change	a little worse	much worse	very much worse

COPD Assessment Test (CAT)

See [ANNEX 3](#)

Physicians' global assessment

Effectiveness of the Tio+Olo FDC 5µg/5µg treatment will be comprehensively assessed (compared to the day before initiation of the Tio+Olo FDC 5µg/5µg) according to the following scale based on the observed symptoms and results of pulmonary function test.

1. Improved, 2.Unchanged, 3.Deteriorated, 4. Not assessable

FVC and FEV1

If the data is available at sites with information of pulmonary medication (i.e. pre-dose or post-dose)

See [ANNEX 2](#) for more details.

#### **9.4 DATA SOURCES**

Case Report Forms (CRFs) for individual patients will be provided by the sponsor via the Electronic Data Capture (EDC) system.

In EDC system, two casebooks will be set up; Book 1 includes baseline, 4 weeks, and 12 weeks. Book 2 includes 24 weeks and 52 weeks.

The data are to be transmitted immediately after being entered into EDC at 12 weeks (Book 1) and 52 weeks (Book 2) after the start of treatment or at discontinuation.

For any adverse events, the data should be immediately entered into EDC and transmitted.

#### **9.5 STUDY SIZE**

Study size is 1000 patients with chronic obstructive pulmonary disease (chronic bronchitis, emphysema) analysed (safety analysis set). As approximately 10 % of the patients are assumed to drop out without any data (just registered), therefore, 1100 patients is planned to be registered.

This is a descriptive study and no confirmatory tests are planned.

The proportion of overall patients with serious cardiovascular events was 2.6% in Tio+Olo FDC 5µg/5µg group in the pooled data of trials 1237.5, 1237.6 and 1237.22. With 1000 patients, the 95% confidence interval of serious cardiovascular events could be estimated with a width of 2.0% to 2.8% (Wilson interval) if the proportion of patients with serious cardiovascular events is between 2.6% and 5.2%.

If the true proportion of patients with serious cardiovascular events is assumed to be 2-fold (i.e., 5.2%), the sample size of 873 is required to have 98% power for rejecting the null hypothesis of incidence=2.6% by using one sample chi-square test with a 0.05 two-sided significance level.

## 9.6 DATA MANAGEMENT

Patients' data will be gathered by EDC system provided by external vendor below.

	Contract 1	Contract 2
Company Name		
Outsourced work	EDC system setting Patient registration Clinical Data Management	Document management of contract with site.

## 9.7 DATA ANALYSIS

This is an observational study to collect real-world data (i.e., data under routine medical practice) on safety and effectiveness of Tio+Olo FDC 5µg/5µg treatment. Analyses are descriptive in nature, including confidence intervals. Due to the nature of the observational study, no confirmatory statistical testing is foreseen in this study. Subgroup analyses are also performed if sample size allows.

Per local regulation, any patient who meets one of the following criteria is treated as ineligible for all analyses:

- No safety observation was documented after registration.
- No required registration procedure was followed.
- No valid site contract was available.

